IRB Approved May 18, 2022

CLINICAL STUDY PROTOCOL

Protocol Number: HBPCOVID02

“A randomized, double-blinded, single-center, phase 2 efficacy, and safety study of allogeneic HB-adMSCs for the treatment of patients with Chronic Post-COVID-19 Syndrome.”

IND Number:	027767
Name of Products:	HB-adMSCs – Hope Biosciences adipose-derived mesenchymal stem cells (Allogeneic) or Placebo - Sterile Saline Solution 0.9%
Indication:	Chronic Post-COVID-19 Syndrome
Principal Investigator:	[name] MD Email: [contact]. [contact]
Sponsor Contact:	[name], RPh Clinical Research Associate/Project Manager [contact] [name] [contact] Email: [contact]
Protocol Version:	1.1
Protocol Version Date:	05/May/2022

CONFIDENTIAL

This document and its contents are the property of and confidential to Hope Biosciences Stem Cell Research Foundation. Any unauthorized copying or use of this document is prohibited.

Ethics and Regulatory Compliance Statement

- 1
2
3 The procedures outlined in this protocol are designed to ensure that the Hope Biosciences Stem
4 Cell Research Foundation, and principal investigator(s) abide by the International Conference on
5 Harmonization (ICH) current Good Clinical Practice (cGCP) guidelines, current Good
Laboratory Practice (cGLP) guidelines, the Declaration of Helsinki, and applicable local
regulatory requirements and laws in the conduct, evaluation, and documentation of this study.

Study Summary

Title	“A randomized, double-blinded, single-center, phase 2 efficacy, and safety study of allogeneic HB-adMSCs for the treatment of patients with Chronic Post-COVID-19 Syndrome.”
Short Title	“HB-adMSCs vs. Placebo for the Treatment of Patients with Chronic Post-COVID-19 Syndrome.”
Protocol Number:	HBPCOVID02
Methodology	Randomized, Double-Blind
Phase of Development:	2
Treatment Duration	26 weeks
Study Center	Single Center – Hope Biosciences Stem Cell Research Foundation
General Objectives	To assess the efficacy and safety of multiple intravenous infusions of allogeneic HB- adMSCs vs. Placebo by improving the signs and symptoms associated with Chronic Post-COVID19 Syndrome.
Number of Subjects	80 subjects
Diagnosis	Chronic Post-COVID-19 Syndrome
Study Product, Dose, Route, Regimen.	Active Product: HB- adMSCs (Hope Biosciences adiposederived mesenchymal stem cells - allogeneic) Dose: 200 million Route: Intravenous Regimen: Weeks 0, 2, 6 and 10. Placebo: Saline Solution 0.9% Dose: N/A Route: Intravenous Regimen: Weeks 0, 2, 6 and 10.

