Duration of administration	1 hour
Laboratory Samples.	Screening, Week 0, 6, and 26.

	Screening
Visits by Weeks	Week 0 _ Infusion 1
	Week 2 _ Infusion 2
	Week 6 _ Infusion 3
	Week 10 _ Infusion 4
	Week 14 _ Follow Up 1
	Week 20 _ Follow Up 2
	Week 26 – End of Study

“A randomized, double-blinded, single-center, phase 2 efficacy, and safety study of allogeneic HB-adMSCs for the treatment of patients with Chronic Post-COVID-19 Syndrome.”

Objectives

Primary Objectives

- To investigate the efficacy of intravenous infusions of HB-adMSCs (allogeneic) vs. Placebo in patients with Chronic Post-COVID-19 Syndrome as determined by improvements in individual symptom scores of Visual Analog Scale of Neurological Symptoms. (Time frame: Baseline to Week 26).
- To assess the safety of intravenous infusions of HB-adMSCs (allogeneic) vs. Placebo in patients with Chronic Post-COVID-19 Syndrome as determined by the incidence of adverse events or serious adverse events (Time frame: Baseline to Week 26).

Secondary Objectives

- To investigate the efficacy of intravenous infusions of HB-adMSCs (allogeneic) vs. Placebo in patients with Chronic Post-COVID-19 Syndrome as determined by improvements in individual symptom scores of Visual Analog Scale of Non-Neurological Symptoms. (Time frame: Baseline to Week 26).
- To evaluate the efficacy of intravenous infusions of HB-adMSCs (allogeneic) vs. Placebo in patients with Chronic Post-COVID-19 Syndrome as determined by changes in Fatigue Scale (Time frame: Baseline to Week 26).
- To assess the efficacy of intravenous infusions of HB-adMSCs (allogeneic) vs. Placebo in patients with Chronic Post-COVID-19 Syndrome as determined by changes in SF-36 Quality of life self-assessment. (Time frame: Baseline to Week 26).
- To identify the safety of intravenous infusions of HB-adMSCs vs. Placebo in patients with Chronic Post-COVID-19 Syndrome as determined by changes in Patient Health Questionnaire (PHQ-9).

Endpoints

Primary Endpoints

The efficacy and safety primary endpoints of this study will be evaluated by assessing changes from Baseline to Weeks 26 in the following:

- Visual Analog Scale of Neurological Symptoms. VAS are psychometric measuring tools intended to document the characteristics of disease-related symptom severity in individuals. The neurological symptoms included in this scale are (1) extreme fatigue (2) brain fog, (3) headache (4) sleep disturbances (5) loss of taste/smell.

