- Incidence of treatment-emergent Adverse Events (TEAEs) and serious Adverse Events (SAEs).
- Incidence of AEs of special interest (serious or nonserious), including thromboembolic events, infections, and hypersensitivities.
- Changes in laboratory values, vital signs, weight, physical exam results, and medications used to treat Chronic Post-COVID-19 Syndrome.

Secondary Endpoints

The efficacy and safety secondary endpoints of this study will be evaluated by assessing changes from Baseline to Weeks 26 in the following:

- Subject's energy and stamina as evidenced on the Fatigue Assessment form.
- Visual Analog Scale of non -Neurological Symptoms. The symptoms included in this scale are (1) dyspnea at rest and with activity, (2) cough, (3) body aches, and (4) joint pain.
- Subject's quality of life as evidenced by the Short Form 36 Health Survey Questionnaire.
- Subject's level of depression as evidenced by the PHQ 9 scale.

Investigational Plan.

[figure not shown]
This study is a randomized, double-blind, single-center, phase 2 clinical trial to assess the efficacy and safety of multiple HB-adMSCs (allogeneic) vs. Placebo for treating Chronic PostCOVID-19 Syndrome. The trial includes a screening period of up to 4 weeks, a 10-week treatment period, and a safety Follow-up period of 16 weeks after the last investigational product administration.

This clinical trial will be opened to enroll 80 eligible participants diagnosed with Chronic PostCOVID-19 Syndrome. The study team will conduct patient recruitment. If eligible participants are identified based on eligibility criteria, a screening visit will be scheduled. An informed consent form will be given to the study participants and signed before any study procedures. The informed consent form will include information about the clinical trial, and some aspects should be considered during this process.

- The principal investigator or study team will make sure the participant was alert and able to read and understand the language in the consent form.
- The principal investigator or study team will ensure the participant took ample time to read the consent form carefully.
- The principal investigator or study team will make sure the consent form was carefully explained to the participant, and any questions or concerns were addressed before signing the document.

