Clinical evaluators (data analysts and physicians) will be trained to maintain blinding to treatment as best as possible to minimize assessment bias. “Best as possible” means that blinding will be held unless an adverse event or serious adverse event occurs that requires unblinding the physician, which is determined by the DSMB.

Training includes a review of the process of blinding, describing who will be responsible for assigning products for the appropriate group, labels that will be used to identify subjects but not treatment group, and the process that should be followed if an adverse event occurs, triggering a review by medical monitor or DSMB.

Prior and Concomitant Medications

Concurrent and prior medications (up to one week before the screening visit) should be recorded in the subject’s medical history at the screening visit. This list of concomitant medications may be updated, if necessary, at the subsequent visits.

It is essential to ask the subject about the start and end date of the current and prior medications. If the subject does not remember the specific date or month, it is recommended to include the approximate year to estimate how long the patient has been taking the medication.

Trial Procedures

The trial includes an up to 28 days screening period, a 10-week Treatment Period, and a 26-week Safety Follow-up Period. All periods are associated with evaluations and procedures that must be performed at specific time points, as represented in Table 1 Schedule of Assessments.

Trial Schedule of Assessments.

Table 1 Schedule of Assessments.

	Visit 1	Randomization	Visit 2	Visit 3	Visit 4	Visit 5	Visit 6	Visit 7	Visit 8
Visit Names	Screening		INF 1 Baseline	INF 2	INF 3	INF 4	Follow Up 1 Phone Call	Follow Up 2 Phone Call	EOS
Window Period	Up to 28 days		± 7 days	± 7 days	± 7 days	± 7 days	± 7 days	± 7 days	± 7 days
Visit Weeks	N/A		0	2	6	10	14	20	26
Informed Consent	X								
Demographics	X								
Medical History	X		X	X	X	X	X	X	X
Concomitant Medications	X		X	X	X	X	X	X	X
Eligibility Criteria	X								
Vital Signs	X		X	X	X	X			X
Weight	X		X	X	X	X			X
Height	X								
Laboratory Samples	X		X			X			X
Physical Examination	X		X	X	X	X			X
Visual Analog Scale of Symptoms	X		X	X	X	X			X
Fatigue Scale	X		X	X	X	X			X
SF-36			X			X			X
PHQ-9	X		X	X	X	X			X
Pre-medications			X	X	X	X			
Study Treatments Administration			X	X	X	X			
24 hours Telephone Encounter			X	X	X	X			
AE and SAE assessments			X	X	X	X	X	X	X

- INF indicates Infusion in visit names.

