All adverse events that do not meet any of the criteria for serious should be regarded as *nonserious adverse events*.

Adverse Event Reporting Period

The study period during which adverse events must be reported is typically defined as the period from the initiation of any study procedures to the end of the study treatment follow-up. For this study, treatment follow-up is described as approximately 16 weeks following the last administration of study treatment.

Stopping Rules

Infusion Stopping Rules

Study treatment infusion will be stopped if a least one of the following events occurs:

1. Allergic reaction as evidenced by severe dyspnea (defined as intense tightening of the chest, air hunger, breathlessness or feeling of suffocation), bronchospasm (defined as coughing, wheezing, difficulty breathing) or hypoxia (defined as pulse oximeter reading of less than 90%) after the product has been administered intravenously.
2. Hypersensitivity reactions such as rash, urticaria, itching, angioedema, nausea, vomiting, hypotension, or any evidence of anaphylaxis.
3. The patient verbally declines the treatment at any moment prior, or during the infusion.
4. Any febrile reaction will be an indicator for pausing the infusion for further evaluation.
5. Malignant Systolic blood pressure (SBP) greater than 170 and/or diastolic blood pressure greater than 100. SBP less than 80mm/Hg and/or DBP less than 40mm/Hg. *
6. Sudden Severe Hypotension (40 mm/Hg drop from infusion starting baseline) or systolic blood pressure <80mmHg.
7. Respiratory distress defined as having an acute sudden onset of shortness of breath or increased work of breathing, SaO₂ less than 90% or a respiratory rate >22 or < 10 breaths per minute. Any increased oxygen support that could indicate imminent respiratory failure.
8. Sudden increase or decrease in pulse rate of 30 bpm or more from infusion starting baseline or an absolute tachycardia of greater than 140 bpm or absolute bradycardia less than 45 bpm.
9. Change in neurologic status from infusion starting baseline including alertness.
10. The Principal Investigator may stop the infusion at any time, based upon PI's discretion.

*Any blood pressure from baseline exceeding or falling below $\pm 20\%$ of baseline or $\geq 140/90$ will necessitate a pause for evaluation.

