Suppose an infusion is stopped for a subject due to an adverse event or serious adverse event, including but not limited to hypersensitivity reaction/anaphylaxis. In that case, no additional study treatment will be given to the study participant who develops the event. Although the study participant will not

receive the investigational product, he or she must be followed for safety purposes according to the protocol.

Study Stopping Rules

This Clinical Trial will stop if any of the following events are present:

1. Subject's Death.
2. Any thromboembolic event will cause a pause in the study until an evaluation can be done by the DSMB, Principal Investigator and Medical Monitor to determine relationship.
3. Any cerebrovascular ischemia or seizure event occurring within 72 hours after any of the investigational product administrations.
4. Any Serious Adverse Events of the following:
 - When there is one CTCAE.v5 grade 4 or 5 AE, irrespective of attribution.
 - Either any CTCAE Grade 2 adverse event that persists for more than two weeks or any Grade 3 adverse event that occurs within 72 hours after product administration.

Should the study participant discontinue study treatment, he/she will be followed for safety according to the protocol safety monitoring plan. The study participant will receive follow-up communication via phone calls or electronically to ascertain the outcome until resolved fully. All will be documented as per protocol.

FDA shall review all changes to the study-stopping rules. If the study is suspended for any reason, it will not be re-opened until FDA agrees. Whether the study is stopped or suspended, all subjects will be followed to the EOS visit.

Statistical Methods

The sample size consists of 80 subjects who have been diagnosed with Chronic Post-COVID-19 Syndrome. All data collected from subjects who are enrolled and received the investigational product will be analyzed. The incidence of Adverse Events and Serious Adverse Events will be recorded and reported. Efficacy will be measured by improving the subject's signs and symptoms associated with Chronic Post-COVID-19 Syndrome. Interim analysis of all safety and efficacy data may be performed at any time deemed appropriate by the Sponsor. Data may be analyzed for internal informational purposes, reports, presentations, and manuscripts.

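### The protocol contradicts itself on how long AEs are collected from participants who receive fewer than four infusions, and one of its rules ends before the Week 26 primary safety time frame

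*Protocol*

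**What the plan says.** The protocol deals with the length of AE collection in several places.

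- **Adverse Event Reporting Period** is the only section that defines when AEs must be reported. The period closes with the end of treatment follow-up, and "treatment follow-up is described as approximately 16 weeks following the last administration of study treatment".
- **Investigational Plan** uses the same anchor: "a 10-week treatment period, and a safety Follow-up period of 16 weeks after the last investigational product administration".
- **Trial Procedures** gives another length: "a 10-week Treatment Period, and a 26-week Safety Follow-up Period".
- **Primary Objectives** sets one time frame for all participants: safety is judged "as determined by the incidence of adverse events or serious adverse events (Time frame: Baseline to Week 26". In agreement with this, **Table 1** places an AE/SAE assessment at every visit from Week 0 to Week 26. The visit descriptions date the Week 14 and 20 calls from the first infusion and the End of Study (EOS) visit from Week 0.
- **Withdrawal Criteria** gives, as its example of leaving the study, a participant who no longer wants the product. Anyone discontinued after at least one infusion is invited to a safety visit, with no date attached.
- **Infusion Stopping Rules and Study Stopping Rules**: a participant whose infusion is stopped for an AE receives no more study treatment and is to be followed for safety as the protocol provides. No week is named. A separate sentence reads "Whether the study is stopped or suspended, all subjects will be followed to the EOS visit".

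In the SAP, the safety analysis set is everyone with at least one dose. Section 5.3.2.2 reports AEs as number of subjects, percentage and number of events.

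**The concern.** A reporting period anchored on the last dose matches a time frame anchored on Week 0 only when all four infusions are given on schedule. For anyone who stops sooner, the two diverge, and the participants affected are not a random subset: hypersensitivity, for example, is a listed reason to stop an infusion, and further study treatment is then barred.

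If a site applied the reporting section literally, an SAE or an event of special interest arising after the cut-off might never be entered. The participant would still count in full in the safety denominator, and the SAP makes no allowance for observation time. Events that were never collected cannot be recovered at the analysis stage.

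**Working it through.** **Inputs.** Infusions at Weeks 0, 2, 6 and 10 (Study Summary: "Regimen: Weeks 0, 2, 6 and 10"). Follow-up of 16 weeks after the last infusion (Adverse Event Reporting Period; Investigational Plan). Alternative follow-up of 26 weeks (Trial Procedures). Safety time frame to Week 26 (Primary Objectives). AE contacts at Weeks 0, 2, 6, 10, 14, 20 and 26 (Table 1). 80 participants randomised 1:1 (SAP 2.2), so 40 per arm.

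**Step 1: the plan's own figure.** For a participant with all four infusions, 10 + 16 = Week 26. This agrees with the objective and with Table 1.

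**Step 2: early stoppers under the reporting section.** End of required reporting = week of last infusion + 16.

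| Last infusion | Reporting ends | Short of Week 26 | AE contacts after that point |
|---|---|---|---|
| 1 (Week 0) | 0 + 16 = Week 16 | 10 weeks (10/26 = 38.5%) | Weeks 20, 26 |
| 2 (Week 2) | 2 + 16 = Week 18 | 8 weeks (8/26 = 30.8%) | Weeks 20, 26 |
| 3 (Week 6) | 6 + 16 = Week 22 | 4 weeks (4/26 = 15.4%) | Week 26 |
| 4 (Week 10) | 10 + 16 = Week 26 | 0 | none |

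**Step 3: the Trial Procedures wording.** A 10-week treatment period plus 26 weeks gives 10 + 26 = Week 36, yet Table 1 has no visit after Week 26. If the 26 weeks are instead counted from each participant's last infusion, the ends are Weeks 26, 28, 32 and 36, and no early stopper falls short. The 16-week and 26-week statements therefore give opposite answers for the same participant.

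**Step 4: does another passage settle it?**
- The instruction to follow a stopped participant as the protocol provides names no week. It can be read as pointing to Table 1 or back to the reporting section.
- The follow-to-EOS sentence depends on the study being stopped or suspended. It does not cover one participant stopping in a study that continues.
- Withdrawal Criteria does not separate stopping the product from leaving follow-up, so Table 1 is no guarantee for those participants.

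**Step 5: size at arm level.** The documents give no discontinuation rate, so 5% to 20% of an arm is an assumption. Planned person-weeks per arm: 40 × 26 = 1,040.
- Low end: 5% of 40 = 2 participants, all stopping after infusion 3: 2 × 4 = 8; 8/1,040 = 0.8%.
- High end: 20% of 40 = 8 participants, all stopping after infusion 1: 8 × 10 = 80; 80/1,040 = 7.7%.

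**The case against.** The best defence is that the 16 weeks merely restate the planned schedule (10 + 16 = 26) in loose wording, while the operative instruction is Table 1. The calls and EOS visit are not dated from the last infusion, each asks about AEs since the previous contact, and stopped participants explicitly remain in safety follow-up. Much of this stands. A reader might infer from the reporting section that early stoppers are in fact observed only to Week 16, 18 or 22. The documents do not support that: they schedule AE assessment to Week 26 and nowhere cancel it for these participants. What remains is that the section defining mandatory reporting says something else, and nothing ranks one passage above the other.

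Three further inferences are tempting but too strong.

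- **That any-AE incidence is substantially under-counted.** If 50% had at least one AE in 26 weeks at a constant rate (an assumption), 16 weeks of observation would give 1 − 0.5^(16/26) = 35%. That does not describe people stopped for an AE, who already count as having one. For people stopping for other reasons, if 10% of an arm left after infusion 1, arm incidence would move only from 50% to 0.9 × 50% + 0.1 × 35% = 48.5%.
- **That thromboembolic events are the group at risk.** Any such event pauses the study, so the follow-to-EOS sentence may apply if a pause counts as suspension. Hypersensitivity is the clearer example.
- **That this rule drives the TEAE tables.** SAP 5.3.2.2 closes the treatment-emergent window on the last day of infusion treatment. That is a separate and tighter limit. The SAE and special-interest summaries are not expressly confined to TEAEs, so they are where a collection gap would show.

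**Conclusion.** The point holds as an internal contradiction about data collection for a primary safety endpoint. It does not show that observation will be cut short. Depending on the passage followed, a participant with fewer than four infusions has AEs collected to Week 16, 18 or 22, to Week 26 or later, or to one undated visit. A site can be compliant and still end collection of new AEs before Week 26.

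Under the assumed 5% to 20% early stopping, the exposure is 0.8% to 7.7% of an arm's person-weeks. It falls mainly on later SAEs, AEs of special interest and additional event types in early stoppers. A bias between arms, and its direction, would require unequal stopping between arms, and the documents give no basis for predicting that. The ambiguity is worth correcting because lost events cannot be retrieved later and the correction is cheap.

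**What to change.** State one data-collection rule in Adverse Event Reporting Period: AEs and SAEs are collected from every dosed participant who has not withdrawn consent to follow-up, through the Week 26 EOS visit or to 16 weeks after the last infusion if that is later, whatever the number of infusions received. The Week 14 and 20 calls and Visit 8 are kept for those who stop early.

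Then bring the other passages into line:
- **Investigational Plan and Trial Procedures**: one follow-up length, consistent with Table 1.
- **Withdrawal Criteria**: separate stopping the product from withdrawing consent to follow-up, and give the safety visit a date.
- **Infusion Stopping Rules and Study Stopping Rules**: refer to the new rule by name where follow-up of a stopped participant is mentioned.

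This concerns data collection only and leaves the criteria for stopping an infusion untouched. The cost is a wording amendment, with the FDA and IRB agreement that the protocol requires for any change, and keeping already scheduled contacts for the few who stop early.

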Sampling tubes, material for shipments of the samples, and a laboratory manual detailing all sample collection and shipment procedures will be provided and distributed to the clinical trial site by the selected laboratory. Laboratory samples will be collected as per protocol during Visit 1 – Screening or Visit 2 – Infusion 1 (Baseline), Visit 5 – Infusion 4, and Visit 8 - End of Study.

Adverse Events

Unanticipated Problems Involving Risk to Subjects or Others

Any incident, experience, or outcome that meets all the following criteria:

- Unexpected in nature, severity, or frequency (i.e., not described in study-related documents such as the IRB-approved protocol or consent form, the investigator's brochure, etc.)
- Related or possibly related to participation in the research (i.e., perhaps related means there is a reasonable possibility that the incident experience or outcome may have been caused by the procedures involved in the study.
- Serious (as defined below) ***“Serious” is different than “severe” as reported in the CTC criteria that apply a grade to the AE.***

Adverse Event

An **adverse event** (AE) is any symptom, sign, illness, or experience that develops or worsens in severity during the study. Intercurrent illnesses or injuries should be regarded as adverse events.

Abnormal results of diagnostic procedures are adverse events if the abnormality:

- results in study withdrawal
- is associated with a serious adverse event
- is associated with clinical signs or symptoms
- leads to additional treatment or to further diagnostic tests
- is considered by the investigator to be of clinical significance

Serious Adverse Event

Adverse events are classified as serious or non-serious. A **serious adverse event** is any AE that is:

- fatal
- life-threatening
- requires or prolongs hospital stay
- results in persistent or significant disability or incapacity
- a congenital anomaly or congenital disability
- an important medical event

Important medical events are those that may not be immediately life-threatening but are clearly of major clinical significance. They may jeopardize the subject and require intervention to prevent the other serious outcomes noted above. For example, drug overdose or abuse, a seizure that did not result in an in-patient hospitalization, or intensive treatment of bronchospasm in an emergency department would typically be considered serious.

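### Study stopping rule 4 catches a Grade 2 event lasting over two weeks, but not an equally long Grade 3 event that starts more than 72 hours after an infusion

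*Protocol*

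**What the plan says.** The protocol's Study Stopping Rules open with "This Clinical Trial will stop if any of the following events are present". Four items follow:

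- Item 1 is a participant's death.
- Item 2 is any thromboembolic event, of any grade and at any time. It pauses the study until the DSMB, the investigator and the medical monitor have judged the relationship.
- Item 3 is cerebrovascular ischemia or seizure, within 72 hours of an administration.
- Item 4 is introduced by "Any Serious Adverse Events of the following" and has two bullets. The first reads "When there is one CTCAE.v5 grade 4 or 5 AE, irrespective of attribution". The second names "any CTCAE Grade 2 adverse event that persists for more than two weeks or any Grade 3 adverse event that occurs within 72 hours" after administration.

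Infusions are given at Weeks 0, 2, 6 and 10 (Study Summary). Adverse events are assessed through Week 26 (Schedule of Assessments). Under Adverse Event Reporting Period, "treatment follow-up is described as approximately 16 weeks following the last administration of study treatment". The SAP's safety sections (5.3.2 and 5.3.3) do not restate or change the stopping rule.

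**The concern.** A single-event stopping rule should be at least as strict for the worse of two otherwise identical events. Here the two limbs of the second bullet use different tests. For Grade 2 the test is how long the event lasts; for Grade 3 it is how soon after an infusion the event begins. A late Grade 3 event that does not resolve passes between them.

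Such an event would be recorded, since adverse events are collected to Week 26, but the written rule would not require the study to stop. Infections and hypersensitivities are named events of special interest (Primary Endpoints). A late, persistent Grade 3 infection would meet none of the four study stopping items, while a Grade 2 infection of the same length would meet item 4, provided it is serious if the lead-in requires that.

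**Working it through.** The protocol gives no stopping probability or event rate for this rule, so there is no figure to reproduce. The check is logical, followed by calendar arithmetic.

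**Logic.** Take an event lasting 21 days that keeps the same grade throughout, and read *occurs* as the time of onset. Apply item 4 under each reading of its wording.

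| Grade, onset after infusion | Bullets as written, or serious event if the lead-in governs | Non-serious event if the lead-in governs | 72 hours applied to both limbs |
|---|---|---|---|
| 2, 48 h | stop | no | stop |
| 2, 240 h | stop | no | **no** |
| 3, 48 h | stop | no | stop |
| 3, 240 h | **no** | no | no |
| 4, 48 h or 240 h | stop | no | stop |

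The first results column contains the inversion: at 240 hours the Grade 2 event stops the trial and the Grade 3 event does not. If the lead-in limits item 4 to serious events, the inversion remains among serious events. It disappears only in the last column.

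**Other items.** Items 1 and 3 do not reach a non-fatal event after 72 hours. Item 2 reaches it only if it is thromboembolic.

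**Calendar.** Nominal infusion days are 0, 14, 42 and 70; end of study is day 26 × 7 = 182.

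- Days inside the 72-hour windows (0–3, 14–17, 42–45, 70–73): 4 × 3 = 12.
- Latest onset for an event to reach two weeks by Week 26: 182 − 14 = 168. Onset days outside the windows: 168 − 12 = 156, and 156/168 = 93%.
- Latest onset to reach two weeks before the Week 10 infusion: 70 − 14 = 56. Window days to that point: 3 × 3 = 9. Outside: 56 − 9 = 47, and 47/56 = 84%.
- Of the 156 days, 168 − 73 = 95 fall after the participant's last window.

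**Cost of closing the gap, illustration only.** The rates here are assumptions. Let p be the chance that a participant already meets the rule, and q the added chance of a newly covered Grade 3 event. With 80 independent participants, the chance of at least one trigger is 1 − (1 − p)^80 before the change and 1 − (1 − p − q)^80 after it.

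| p | Before | After, q = 0.1% | After, q = 0.5% |
|---|---|---|---|
| 1% | 55.3% | 58.7% | 70.2% |
| 2% | 80.1% | 81.7% | 86.8% |
| 5% | 98.4% | 98.5% | 98.9% |

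Within this range the increase runs from 0.1 points (98.35% to 98.48%) to 14.9 points (55.25% to 70.15%).

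**The case against.** The strongest reply is that the gap is narrow and other provisions cover much of it.

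- *Thromboembolic events.* Item 2 pauses the study for any of these, whatever the grade or timing. This stands. A reader might infer that a late Grade 3 event is protected only by discretion. The documents do not support that for thromboembolic events.
- *Changing grade.* An event that worsens to Grade 4 meets the first bullet. One that eases to Grade 2 and then lasts over two weeks arguably meets the Grade 2 limb. This also stands; the gap concerns events that stay at Grade 3.
- *The 72-hour phrase might govern both limbs.* The inversion would then go, because neither late event would count. But the phrase attaches to *occurs* in the Grade 3 limb, so this is the weaker reading.
- *Staff would read Grade 2 as Grade 2 or higher.* They might, but a separate Grade 3 limb points the other way. If that was the intent, the change only writes it down.
- *Other powers exist.* The sponsor may discontinue the trial for safety (Withdrawal Criteria), and "The Principal Investigator may stop the infusion at any time". Blinding for Clinical Evaluators also mentions adverse events that trigger review by the medical monitor or DSMB. These are useful but do not replace a listed trigger.
- *A stop need not be final.* Item 2 is only a pause, and the section allows re-opening after suspension with FDA agreement. This stands.

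A reader might also infer that the lead-in contradicts the bullets, since the lead-in speaks of serious events and the bullets of any adverse event. The protocol does separate the two ideas: it distinguishes serious from severe, "as reported in the CTC criteria that apply a grade to the AE", and says "All adverse events that do not meet any of the criteria for serious should be regarded as" non-serious. But that separation lets both conditions apply together, as serious and of the listed grade. It is an ambiguity, not a contradiction. Likewise, waiving attribution only in the first bullet leaves a question about the second without showing an error.

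**Conclusion.** The point holds as a defect of wording. On the natural reading, an event that is not thromboembolic, starts more than 72 hours after an infusion and remains at Grade 3 for over two weeks meets no study stopping rule, while a Grade 2 event of the same onset and length meets item 4. It does not depend on how the serious-event lead-in is read.

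The conclusion assumes that *occurs* means onset, that the 72-hour phrase belongs to the Grade 3 limb alone, and that *Grade 2* means exactly Grade 2. The calendar shares also assume nominal visit days.

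The 93% and 84% figures show how much of the schedule the Grade 3 limb leaves uncovered. It is tempting to take them as the chance that a harmful event is missed, but the documents give no Grade 3 rate and onset need not be spread evenly over time. For the 95 days after a participant's last window, a stop could protect only other participants who are still being dosed.

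**What to change.** In the first limb of item 4's second bullet, insert *or higher* after *Grade 2*, so that the two-week duration test covers every grade from 2 upward. Leave the 72-hour Grade 3 limb and the first bullet unchanged. This also settles the case of an event that moves between Grades 3 and 2 over more than two weeks.

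The change makes a stop somewhat more likely. By how much is unknown, because it depends on event rates that the documents do not give; the illustration above shows it could be negligible or noticeable. It needs an amendment to one list item, with FDA and IRB agreement (Protocol Amendments); the Study Stopping Rules already require FDA review of such changes.

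Two questions should go to the sponsor separately: must second-bullet events be serious, and does attribution matter there? Neither is needed to close the gap. Answering them by rewording the lead-in or waiving attribution could widen a rule that one event can trigger, so this point does not propose either.
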